Interim Analysis	An unblinded analysis team (separate and firewalled from the study team) will be responsible for the conduct of the Interim Analysis rather than a member of the Strategic Medical Affairs department	As the analysis will be used to make a go/no go decision on study conduct, a rigorous approach to the analysis is warranted.

3 The Study Objectives

The primary objective of this study is determine whether two intra-articular injections of MONOVISC, separated by 1 month, are superior to two intra-articular injections of physiologic saline, separated by 1 month, in relieving hip osteoarthritis pain, as determined by reduction in walking pain change from baseline.

We hypothesize that two (2) monthly injections of MONOVISC will be an effective treatment regimen for hip OA patients.

4 Study Design

This study is a prospective, multi-center, double-blinded, randomized, controlled, superiority study comparing intra-articular injections of MONOVISC High Molecular Weight Hyaluronan with intra-articular injections of physiologic saline. The study will take place in the United States, with up to 25 investigational sites. Subjects will be randomized through a 2:1 schema to receive either two (2) injections of 4 ml of MONOVISC, separated by 1 month (active treatment), or two (2) monthly injections of 4 ml of saline, separated by 1 month (control treatment).

Subjects will return for follow-up visits at 2, 4, 8, 16, and 26 weeks after the first injection.

The primary endpoint will be pain during walking (WOMAC A1) change from baseline at the 26 week time point.

An interim analysis (IA) of the primary endpoint will be conducted after 74 MONOVISC and 37 saline subjects have received both injections of MONOVISC or saline and completed their per protocol 26 week follow up visit. A stopping rule for futility will be implemented, such that the study will be terminated if the improvement of MONOVISC over saline (change from baseline) is less than 0.4 on a 10 point Numerical Rating Scale (NRS) in both the Per Protocol Analysis Set for the 26 week interval and the As Treated Analysis Set for the 26 Week interval. If the improvement of MONOVISC over saline (change from baseline) is more than 0.4 NRS in either of these analysis sets, the study will continue to completion. Details of planned analyses are provided in Section 14.

5 Treatment Assignment

The treatment groups in this study are:

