The primary efficacy endpoint analysis will be conducted on the MITT Analysis Set, which consists of all primary endpoint data on all As Treated (AT) subjects (regardless of whether or not there were protocol deviations associated with the data) for the 2, 4, 8, 16 and 26 week visits. In this MITT Analysis Set, missing primary endpoint data for the 26 Week visit will be imputed with multiple imputation methodology using SAS PROC MI with the regression method and a monotone missing data pattern.

No imputation of missing data will be performed for visits other than the 26 Week visit.

9 Primary and Secondary Endpoints

The primary and secondary endpoints are derived from the Western Ontario and McMaster Universities Arthritis Index (WOMAC), which is widely used in the evaluation of Hip and Knee Osteoarthritis. The WOMAC is available in over 65 languages and has been linguistically validated. It is a self-administered questionnaire consisting of 24 items divided into 3 subscales, A, B, and C: A) Pain (5 items), B) Stiffness (2 items), and C) Physical Function (17 items). The overall WOMAC score is determined by summing the scores across the 3 subscales and the score ranges include 0–24 (derived from the NRS scale). Higher scores on

the WOMAC indicate worse pain, stiffness, and functional limitations. Specific scoring details will be provided in the table shells document referenced in Section 15.

The WOMAC A is the pain subscale of the WOMAC questionnaire. Again, response options for individual questions are 0 through 10, where 0 indicates no pain and 10 indicates worst possible pain. The WOMAC A pain subscale scores ranges are 0-50 NRS.

WOMAC A1 is the first question of the WOMAC A and specifically addresses pain during walking. Response options are 0 through 10 NRS, where 0 indicates no pain and 10 indicates worst possible pain.

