For each follow-up time point (the 2, 4, 8, 16 and 26 Week visits), a flowchart, as shown in Figure 2, will be created. The flowchart will present the Safety Analysis Set, the As Treated Analysis Set, and the Per Protocol Analysis Set for the Time Point. This diagram will indicate all protocol violations, deaths, withdrawals of consent, and Subjects who are past due for follow-up in the interval.

Figure 2 Example of Analysis Set Flow for a Specific Time Point

A Medically Trained Professional and a Biostatistician at DePuy Synthes will review and confirm all protocol non-compliances prior to the IA data cut, and also prior to Final dataset lock. The Analysis Sets constructed for the IA will be designated as “IA” as they will differ from the Final (end of study) Analysis Sets.

12 Sample Size Justification

The sample size was determined based on the primary endpoint, which is a superiority comparison of WOMAC A1 walking pain change from baseline at 26 Weeks for MONOVISC Subjects compared to Saline Subjects. Although it is planned to conduct the primary endpoint analysis with a longitudinal model, and to compare the WOMAC A1 walking pain change from baseline adjusted means at 26 Weeks from this longitudinal model, the sample size was established based upon estimates for a t-test comparison of 26 week means for simplicity.

Specifically, it is anticipated that the mean difference in WOMAC A1 walking pain change from baseline means will be at least 0.6 (where the mean for MONOVISC subjects is less than the mean for Saline Subjects), and that the standard deviation in WOMAC A1 walking pain change from baseline at 26 weeks will be approximately 2.2 in both groups. This standard deviation of 2.2 is consistent with published studies by Spitzer (2010)² and Qvistgaard (2006)³; also, 2.2 is approximately ¼ of the maximum anticipated range of WOMAC A1 walking pain change from baseline, which would be an estimate of the standard deviation from data which are normally distributed. Using a two-tailed t-test and assuming a 2:1 randomization, the required sample size to yield 80% statistical power was estimated to be 318 MONOVISC and 159 Saline. With an anticipated attrition rate of 15%, the total study population was increased to be 560 patients (374 MONOVISC, 186 Saline). The sample size estimate was calculated with the following SAS code.

Figure 3 SAS Code for Power Estimation: WOCAC A Pain at 26 Weeks

```
proc power;
  twosamplemeans
  meandiff= .6
  stddev=2.2

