13.4 Efficacy Evaluations

13.4.1 Primary Endpoint Analyses

The primary endpoint analysis will be conducted with a longitudinal model on the MITT Analysis Set using PROC MIXED. The model will include absolute change from baseline in WOMAC A1 as the dependent variable, treatment (MONOVISC versus Saline) and visit (Week 2, Week 4, Week 8, Week 16, and Week 26) as fixed effects, and subject as a random effect. In the model, visit will be treated as class variable and an antidependence covariance matrix will be assumed to model the within-subject variability between visits. The antidependence structure allows the correlation between different time periods to vary. Denominator degrees of freedom will be estimated using the Kenward–Roger approximation.

In order to test the robustness of study results to the antedependence model assumptions, the primary endpoint longitudinal analysis will be repeated with two additional covariance structures: autoregressive (AR) and Toeplitz. These analyses will be conducted on the same MITT analysis set which was utilized for the primary endpoint analysis.

With a mixed effects model as the primary analysis model, no imputation of missing data at visits prior to the Week 26 will be done. However, missing data at Week 26 will be imputed, as discussed in Section 8. A supportive analysis of the primary endpoint analysis will be conducted on the Per Protocol Analysis Set for Longitudinal Analysis with the same longitudinal model.

Age, Gender, and pre-injection WOMAC A1 pain score will be compared between treatment groups and if they are found to be significantly different ($p<0.05$) in the As Treated Analysis Set at 26 weeks, then an additional sensitivity analysis will be conducted for the primary endpoint analysis. In this analysis, fixed effects for Age, Gender, and the continuous baseline value of WOMAC A1 will be added, but otherwise the model will remain the same.

If marked differences are observed between the results obtained with the primary longitudinal model and any of the sensitivity analysis, they will be reported and addressed in the Clinical Study Report.

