13.4.2 Secondary Endpoint Analyses

The secondary endpoints are the WOMAC A1 walking pain change from baseline at each post-baseline time point: 2, 4, 8, and 16 Week. Each of the secondary endpoints will be analyzed utilizing the primary longitudinal model described in the Primary Endpoint Analysis (Section 13.4.1). A gate-keeping procedure will be implemented to control the family-wise Type 1 Error (see Section 6.1), thus the secondary endpoints will be tested in sequence only provided as a statistically significant result was obtained in the previous test.

If any of the sensitivity analyses conducted on the primary endpoint produces results which differ substantially from the primary analysis, the sensitivity analyses will be repeated on all secondary endpoints.

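### The covariance sensitivity analyses (AR and Toeplitz) are a weak test of the antedependence assumption; an unstructured run would be a cheap improvement

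*SAP*

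**What the plan says.** SAP 13.4.1 fits the change in WOMAC A1 with treatment and visit "as fixed effects, and subject as a random effect". For the repeated measures, "an antidependence covariance matrix will be assumed to model the within-subject variability between visits". The order of antedependence is not given.

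The purpose of the check is explicit: "In order to test the robustness of study results to the antedependence model assumptions". The method is that "the primary endpoint longitudinal analysis will be repeated with two additional covariance structures: autoregressive (AR) and Toeplitz". The SAP gives neither the order of these structures nor whether they are homogeneous or heterogeneous in variance, and it does not say whether AR is adapted to visit spacing. It plans no unstructured covariance and no empirical standard error. The per-protocol analysis and the conditional covariate analysis keep the same covariance model, and SAP 13.4.3 plans nothing further for these endpoints.

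Two things follow from the reruns. Marked differences must be reported and addressed in the study report (SAP 13.4.1). If results differ substantially, "the sensitivity analyses will be repeated on all secondary endpoints" (SAP 13.4.2).

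On timing, SAP Section 4 says "Subjects will return for follow-up visits at 2, 4, 8, 16, and 26 weeks after the first injection"; the schedule in Protocol 1.1 puts these visits at days 14, 28, 60, 120 and 180. At week 26, "missing primary endpoint data for the 26 Week visit will be imputed with multiple imputation methodology" (SAP Section 8). Protocol 11.10 names antedependence only.

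**The concern.** A sensitivity analysis tests an assumption only if it relaxes that assumption. First-order antedependence leaves the variance free at each visit and lets adjacent correlations differ. What it restricts is the correlation between non-adjacent visits, which must equal the product of the adjacent correlations in between. A useful check would free those longer-lag correlations and leave the variances alone.

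AR does the opposite: it keeps the product rule and adds restrictions. Toeplitz frees the longer lags, but in its ordinary form it also pools the variance and makes correlation depend only on visit number. Lag 1 then covers gaps of 14, 32, 60 and 60 days.

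At stake is how the reruns are read. Agreement with AR says little about antedependence. A difference under Toeplitz could come from the correlation assumption or from variance pooling. The study could claim robustness it has not shown, or repeat the secondary analyses because of an artefact.

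**Working it through.** **Inputs from the documents.** Week-26 SD 2.2 in both groups; 318 MONOVISC and 159 Saline evaluable; difference 0.6; two-sided 5% (SAP Sections 6 and 12). Visit days from Protocol 1.1.

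**Assumptions.** The SDs before week 26 and all correlations, since the documents give none. First-order antedependence. AR(1) and Toeplitz in homogeneous form. Complete data. No random subject effect unless stated. Steps 3 and 5 take a week-26 treatment difference estimated separately at that visit; SAP 13.4.1 writes no treatment-by-visit term, so step 4 also looks at the model as written.

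**1. The plan's own figure.** A two-sample t-test with difference 0.6, SD 2.2 and 2:1 allocation needs 159 Saline and 318 MONOVISC, 477 in all. Power at 318/159 is 0.8002. The stated figure reproduces.

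**2. Which structure is nested in which.** Write s_i for the SD at visit i, r_k for the correlation between visits k and k+1, and c_m for the correlation at lag m.
- First-order antedependence: V_ij = s_i s_j × product of r_k from i to j−1. Parameters: 5 + 4 = 9.
- AR(1): the same formula with every s_i = s and every r_k = r. Parameters: 2. It is a special case, and remains one if a random subject effect is added to both models.
- Toeplitz: V_ij = s² × c_|i−j|. Parameters: 1 + 4 = 5. Lags 2 to 4 are free of the product rule, so it is not nested in antedependence.
- Unstructured: 5 × 6 / 2 = 15 parameters. It contains all of the above.

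**3. Week-26 standard error under pooled variance.** The correct value is 2.2 × √(1/318 + 1/159) = 2.2 × 0.0971 = 0.214. Homogeneous AR(1) and Toeplitz replace 2.2 by approximately the root mean of the visit variances. The implied type I error of the rerun is 2 × (1 − Φ(1.96 × ratio)).

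| Assumed SDs, week 2 to week 26 | Mean variance | Pooled SD | SE | Ratio to 0.214 | Type I error of the rerun |
|---|---|---|---|---|---|
| 1.8, 1.9, 2.0, 2.1, 2.2 | 20.10/5 = 4.02 | 2.005 | 0.195 | 0.91 | 7.4% |
| 2.2 throughout | 4.84 | 2.2 | 0.214 | 1.00 | 5.0% |
| 2.6, 2.5, 2.4, 2.3, 2.2 | 28.90/5 = 5.78 | 2.404 | 0.234 | 1.09 | 3.2% |

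Full likelihood fits of AR(1) and Toeplitz give the same SEs to three decimals. Antedependence and unstructured both give 0.214 in all three rows.

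**4. Can Toeplitz detect a first-order failure?** Take a flat SD of 2.2 and correlation 0.6 between every pair of visits, which breaks the product rule. Use the model as written, with one treatment effect common to all visits.
- Antedependence and AR(1) both fit r = 0.6. The variance factor is (1 + 0.6)/(5 − 3 × 0.6) = 0.5, so the model SE is 0.214 × √0.5 = 0.151.
- Their weights are 0.3125 on the first and last visits and 0.125 on the other three. The true variance factor is 0.6 + 0.4 × (2 × 0.3125² + 3 × 0.125²) = 0.697, so the true SE is 0.214 × √0.697 = 0.178. The ratio is 0.85.
- Toeplitz weights the visits equally here: (1 + 4 × 0.6)/5 = 0.68, so the SE is 0.214 × √0.68 = 0.176, which is correct.

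AR repeats the primary model's error exactly; Toeplitz exposes it.

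**5. Heterogeneous forms.** Letting the variance differ by visit removes the pooling error. If adjacent correlations also differ (for example 0.85, 0.75, 0.65, 0.65), heterogeneous AR and Toeplitz still give week-26 SEs of 0.227 to 0.231, which is 6% to 8% too large. Unstructured gives 0.214.

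**6. The random subject effect.** It adds a constant to every entry of V. Toeplitz can already absorb a constant, so the two are not separately identifiable. Antedependence plus that constant is no longer pure antedependence. In one scenario (correlation 0.6 throughout, SDs rising from 1.8 to 2.2, random effect kept) the primary week-26 SE is 0.206, about 3.5% low, while AR and Toeplitz give 0.195.

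**The case against.** Three stronger readings are tempting, and the documents support none of them.

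- **That the two reruns cannot test antedependence at all.** This is true of first-order AR but not of Toeplitz, as step 4 shows. The fault in Toeplitz is that it changes two things at once.
- **That the SAP forces equal variances.** It names AR and Toeplitz without a variance form, and heterogeneous versions are not excluded. What is certain is that the form is unstated. The 9% figures apply to the ordinary, homogeneous forms.
- **That the trial's type I error is about 7%.** Success rests on the primary longitudinal model alone (Protocol 11.7, SAP Section 10). With complete data and a visit-specific contrast, antedependence gives the correct week-26 SE in every case examined without the random effect. The 7.4% describes a rerun that carries no success criterion, and under falling SDs the same calculation gives 3.2%.

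It is also fair to say that the overlap between Toeplitz and the random subject effect concerns how the variance is split. The marginal covariance, and hence the treatment SE, is unaffected. It is a fitting and convergence warning, not a bias.

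All of this stands. It limits the size of the point but does not remove it: one of the two planned checks cannot do the stated job, and the other does it only in part.

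**Conclusion.** The point holds as a cheap improvement. First-order AR cannot challenge first-order antedependence. Toeplitz can, but its ordinary form mixes that test with pooled variance and lag-only correlation over unequally spaced visits.

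If SDs differ by visit, the reruns misstate the week-26 SE in either direction: by about 9% for a change of 0.4 NRS in SD between week 2 and week 26, and not at all if SDs are flat. The direction cannot be known from the documents. The size rests on assumed SD paths, homogeneous forms, complete data and a visit-specific contrast.

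The consequence falls on the robustness statement and on the trigger in SAP 13.4.2, not on the primary success criterion. The one scenario in which the primary SE itself moved (3.5%, with the random subject effect kept) is modest, and is a further reason to have a run that imposes no structure.

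**What to change.** In SAP 13.4.1, replace the AR rerun with an unstructured covariance: TYPE=UN on the REPEATED statement, without the RANDOM subject effect, which is redundant there. With 15 parameters and about 477 evaluable patients it should be feasible. It gave the true SE in every scenario examined.

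Toeplitz may stay as a second check, in heterogeneous form and without the random subject effect. State its variance form and the order of antedependence in the primary model.

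Spatial power on study day should not be the replacement. It handles spacing, but it has a single variance, and its correlations ρ^|t_i − t_j| obey the same product rule, so it too is a special case of first-order antedependence.

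Making unstructured the primary covariance is optional and would also touch Protocol 11.10.

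Cost: one SAP sentence, a few lines of code, and five or six more covariance parameters than the primary model (15 against 9, or 10 with the random subject effect), fitted in each imputed dataset.

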6.3 Study Population

This study will be restricted to adult patients with mild to moderate hip osteoarthritis, as measured by Kellgren/Lawrence score. Up to 560 patients will be treated in a 2:1 randomization scheme. Such patients have been shown to derive the greatest benefit from HA therapy in previous studies of patients with knee OA, and are the indicated patient population for currently marketed HA therapies. Only patients with K-L Grades 2 and 3 hip OA will be included in the trial, such that beginning and end stage OA patients are excluded. Also, only patients reporting NRS walking pain of ≥ 4 and ≤ 8 will be included. These pain states were chosen to exclude patients with only minimal pain that can be addressed with conservative therapy, as well as those with end stage disease that are not likely to respond to HA therapy.

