8.5 Baseline / Randomization / Injection #1 (Day 0, Visit #2)

Baseline assessment, patient randomization and Injection #1 must be performed within 30 days of the screening visit, and should be performed on the same day

The following will be performed after the subject has signed the EC/IRB approved Informed Consent form:

A review and reconfirmation of the Inclusion/Exclusion criteria obtained at the initial screening visit will be completed by a designated member of the study team. Confirmation that subject has complied with the washout period for all pain medications for a period of at least 7 days, and 48 hours for acetaminophen, will be documented. In addition, if subject is a female of childbearing potential, she must have a negative pregnancy test, or document her inability to become pregnant (e.g. surgically sterile). Confirmation of K-L grade 2/3 hip OA should be performed before the baseline visit. Subjects who maintain study qualification will be randomized to receive either MONOVISC or Saline.

Evaluation Assessment by either the ***Injecting*** or ***Blinded*** Investigator (see section 12.1.1): A complete evaluation will be documented on the Screening CRF. Data collection and procedures will include:

- General medical exam
- Work status
- Current medication consumption

Each subject will then complete the following self-report questionnaires:

- Western Ontario MacMaster (WOMAC)
- Patient Global Assessment (PGA)
- SF-12

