11.10 Analysis Plan

All statistical processing will be performed using SAS® Version 9.2 or higher, unless otherwise noted. A separate Statistical Analysis Plan (SAP) document that provides greater detail on data derivations and the analyses to be performed will be developed within 90 days after the first patient is enrolled.

Summary tables will be provided for subject demographics and baseline variables for the Safety Analysis Set, the As Treated Analysis Set at 26 weeks, and the Per Protocol Analysis Set at 26 weeks. Safety endpoints (adverse events) will be summarized on the Safety Analysis Set. Effectiveness endpoints will be summarized at each protocol-specified evaluation time point on the Per Protocol Analysis Set for the time point. Analyses will be conducted on pooled data from all sites. For the primary endpoint data at 26 weeks, a 2-way ANOVA test with interaction term will be conducted to confirm the homogeneity of 26 week data across sites. The primary endpoint analysis will be conducted with a longitudinal model on the MITT Analysis Set using PROC MIXED and an antedependence covariance structure to model the correlation between visits. A supportive analysis of the primary endpoint analysis will be conducted on the Per Protocol Analysis Set for Longitudinal Analysis with the same PROC MIXED model.

Descriptive statistics for dichotomous/categorical variables will include the number and percentage of subjects. Fisher's exact test 2-sided *p*-values will be provided for the comparison of dichotomous variables, including adverse event rates, to facilitate clinical judgment. Descriptive statistics for continuous variables will include the number of subjects, mean, standard deviation, median, minimum, and maximum. *P*-values for comparing continuous endpoints will be provided to facilitate clinical judgment; these will be 2-sided *p*-values based upon the t-distribution.

If Age, Gender, or pre-injection WOMAC A1 pain score are found to be significantly different (*p*<0.05) across treatment groups in the As Treated Analysis Set at 26 weeks, then an ANCOVA sensitivity analysis will be conducted for the primary endpoint analysis (on the MITT Analysis Set, with Age, Gender, and pre-injection WOMAC A1 pain as covariates).

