6.1 Control of Type 1 Error

Family-wise control of Type I Error across all primary and secondary endpoints will be accomplished using the following gatekeeping strategy which is depicted in Figure 1.

If the study is successful and the primary endpoint analysis demonstrates a statistically significant difference (favoring MONOVISC vs. Saline) at 26 Weeks, then we will test the WOMAC A1 change from baseline at 16 Weeks for a significant difference (favoring MONOVISC vs. Saline). If this is successful, we will test the difference at 8 Weeks; if this is successful, we will test the difference at 4 Weeks; and if this is successful, we will test the difference at 2 Weeks. At any point, if one of these comparisons fails to be statistically significant, then we will cease further testing in the specified order. Each of these tests will be conducted utilizing the primary endpoint analysis on the Modified Intent to Treat Analysis Set for Longitudinal Analysis. We will test each of the secondary endpoints with a 2-sided p-value against threshold of 0.05 (a 2-sided 5% alpha) with no further adjustment for multiplicity.

Further detail of the hypotheses tested is found in Section 10.

Figure 1 Primary and Secondary Gatekeeping Procedural Flow

Note: The hypothesis tests indicated above are to be performed on the endpoints which we have specified as primary and secondary, WOMAC A1 change from baseline at 26 (primary) weeks and also at 2, 4, 8, and 16 weeks.

7 Interval Windows

The study windows are presented in the Time and Events Schedule (CSP Section 1.1).

For analysis purposes, the baseline/screening evaluation is to be done within 30 days prior to the first injection; the first injection is considered to be day 0. The 2, 4, 8, 16 and 26 Week visits will occur in the time intervals (days) indicated in Table 2, below.

Table 2 Study Interval Windows

Analysis Visit Label	Nominal Study Visit	Study Interval
Baseline	Baseline/Screening	-30 to 0
2 Week	Day 14 ± 7 days	11 to 17
4 Week	Day 28 ± 7 days	21 to 35
8 Week	Day 60 ± 14 days	46 to 74
16 Week	Day 120 ± 14 days	105 to 134
26 Week	Day 180 ± 14 days	159 to 201

Note:

Day 0 is defined as the Study Day of first injection.

Baseline is defined as the last non-missing assessment prior to first injection.

Baseline must occur no more than 30 days after Screening.

8 Handling of Missing Data

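### Baseline walking pain is left out of the primary model and is adjusted for only if a balance test is significant, so precision may be given up

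*SAP*

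**What the plan says.** SAP 13.4.1 takes absolute change from baseline in WOMAC A1 as the outcome and lists "treatment (MONOVISC versus Saline) and visit (Week 2, Week 4, Week 8, Week 16, and Week 26) as fixed effects", with subject as a random effect. No baseline term appears. The four secondary endpoints use the same model (SAP 13.4.2), and SAP 13.4.3 plans no further efficacy analysis of the primary or secondary endpoints.

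Baseline enters only through a conditional sensitivity analysis. The SAP's condition reads "Age, Gender, and pre-injection WOMAC A1 pain score will be compared between treatment groups and if they are found to be significantly different" at p<0.05 in the As Treated set at 26 weeks. If it is met, "fixed effects for Age, Gender, and the continuous baseline value of WOMAC A1 will be added, but otherwise the model will remain the same". Protocol 11.10 has the same rule with a different conjunction: "If Age, Gender, or pre-injection WOMAC A1 pain score are found to be significantly different". SAP Section 11 defines the As Treated set by having a visit in the interval, so the test is run on subjects who attended at week 26.

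Missing week-26 values are "imputed with multiple imputation methodology using SAS PROC MI with the regression method and a monotone missing data pattern" (SAP Section 8). No predictors are named.

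The measurement itself is available. Protocol 8.5 has the WOMAC completed at Visit 2, before the first injection, and a note in SAP Section 7 says "Baseline is defined as the last non-missing assessment prior to first injection".

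**The concern.** A change score with no baseline term is a regression of the week-26 score on baseline with the slope set to 1 instead of estimated. If the true slope is b, two things follow. The residual variance is larger than it need be, and (1 − b) times any chance baseline difference between arms stays in the treatment estimate.

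The trigger does not repair this. A balance test measures chance imbalance, not how strongly baseline predicts outcome; baseline can be highly informative in a well-balanced trial, where the trigger stays silent. The test is also run on a post-randomization subset, and its wording differs between the two documents.

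SAP 13.8 adds a tertiary analysis of the raw WOMAC A1 score with a similar model. Without a baseline term, the raw-score and change-score effects can differ simply because the arms differed at baseline. With baseline and baseline-by-visit in both models they coincide.

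What is at stake is the width of the primary and secondary confidence intervals and how far chance imbalance moves the estimate. Type I error is not at stake.

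**Working it through.** **Inputs from the documents** (SAP Section 12, Protocol 11.9): difference 0.6, change-score SD 2.2, two-sided alpha 0.05, 318 + 159 = 477 completers.

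**The plan's figure.** √(1/318 + 1/159) = 0.0971, so the SE is 2.2 × 0.0971 = 0.2137 and the noncentrality is 0.6/0.2137 = 2.81 on 475 df. Noncentral-t power is 80.0%. The stated 477 reproduces.

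**Assumed inputs.** The documents give neither the baseline SD (s_b) nor the baseline-to-week-26 correlation (r). I take s_b from 1.2 to 1.5 and r from 0.2 to 0.5. For orientation, Protocol 6.3 states that "only patients reporting NRS walking pain of ≥ 4 and ≤ 8 will be included"; equally likely integer scores 4 to 8 have SD 1.41. That restriction applies to the screening NRS, not to the Visit 2 WOMAC A1, so it is a guide and not a bound.

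**Formulas.** Hold Var(change) = s_b² + s_f² − 2·r·s_b·s_f at 2.2² = 4.84 and solve for the week-26 SD, s_f. Then:
- slope b = r·s_f/s_b
- proportion of variance saved = (s_b − r·s_f)²/4.84
- adjusted power: noncentral t with SD 2.2·√(1 − saving)
- extra unadjusted completers for equal precision = 477/(1 − saving) − 477
- shift from an imbalance of z standard errors = |1 − b|·z·s_b·0.0971

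**Worked case, s_b = 1.2, r = 0.3.** s_f = 0.36 + √(4.84 − 1.44 × 0.91) = 2.239; b = 0.3 × 2.239/1.2 = 0.56; saving = (1.2 − 0.672)²/4.84 = 5.8%; residual SD 2.136; power 82.3%; 29 extra completers. An imbalance at z = 1.96 is 1.96 × 1.2 × 0.0971 = 0.228 NRS, and the shift is 0.44 × 0.228 = 0.10 NRS.

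| s_b | r | slope | variance saved | power | shift at z = 1.96 (NRS) |
|---|---|---|---|---|---|
| 1.2 | 0.2 | 0.35 | 12.6% | 85.0% | 0.149 |
| 1.2 | 0.3 | 0.56 | 5.8% | 82.3% | 0.101 |
| 1.2 | 0.4 | 0.80 | 1.2% | 80.5% | 0.047 |
| 1.2 | 0.5 | 1.06 | 0.1% | 80.1% | 0.013 |
| 1.5 | 0.2 | 0.26 | 25.6% | 90.1% | 0.212 |
| 1.5 | 0.3 | 0.42 | 15.4% | 86.1% | 0.164 |
| 1.5 | 0.4 | 0.62 | 6.8% | 82.7% | 0.109 |
| 1.5 | 0.5 | 0.84 | 1.2% | 80.5% | 0.045 |

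At s_b = 1.0 and r = 0.3 the saving is 2.1% and power 80.8%. Gain and shift are both zero where the slope is exactly 1.

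**Size of the shift.** A baseline difference just under the trigger (0.23 to 0.29 NRS) moves the unadjusted effect by 0.01 to 0.21 NRS, or 2 to 35% of 0.6. That is a worst case. At the median chance imbalance (z = 0.674) the shift is 0.005 to 0.07 NRS, or 1 to 12%.

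**How often the trigger fires**, with balanced arms and three independent tests at 0.05: 1 − 0.95³ = 14.3% if any one suffices (the protocol's "or"), and 0.05³ = 0.0125% if all three must differ (the SAP's "and", read literally).

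**The case against.** The strongest reply is that nothing is broken. A prespecified change-score analysis of a randomized trial is legitimate, 477 was planned on the change-score SD, and the triggered analysis never replaces the primary result. All of that stands; any precision gained would be on top of the planned 80%.

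Four further points are fair:

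- **The gain rests on two unstated inputs.** At correlation 0.4 the saving is only 1.2 to 6.8%. The 26% needs SD 1.5 and correlation 0.2 together.
- **The shift and the lost precision are one quantity seen twice.** The SD of the shift equals √saving times the unadjusted SE (0.051 both ways in the worked case). It averages zero over randomizations and is already inside the reported interval, so the two should not be added.
- **The reader is not left blind to imbalance.** Baseline tables are always given. The raw-score model in SAP 13.8 is the slope-0 analysis, so for slopes between 0 and 1 it and the primary estimate should roughly bracket the adjusted one. In one simulated data set the two were −0.490 and −0.449, with −0.470 after adjustment. The adjusted estimate and its tighter interval still go unreported unless triggered.
- **The power figures are for a complete-data comparison at week 26.** They carry over to the longitudinal model only if it estimates a week-26 contrast. SAP 13.4.1 lists no treatment-by-visit term.

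The extra-completers figure also depends on framing. At the 25.6% saving, 164 more unadjusted completers would match the adjusted precision; equivalently, about 477 × 0.744 = 355 adjusted completers would give 80% power.

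These points limit the size of the claim but give no reason to leave baseline out. In large samples the adjusted residual variance cannot exceed that of the change score.

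**Conclusion.** The concern holds, as a matter of efficiency and conditional bias and not of validity. Unconditional type I error is 5% and the stated power is met.

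With change SD 2.2, baseline SD 1.2 to 1.5 and correlation 0.2 to 0.5 (the last two assumed), a prespecified baseline covariate would save about 0 to 26% of residual variance. Power would go from 80% to between 80% and 90%, worth 0 to 164 completers. At correlation 0.5 the gain is negligible.

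As written, the adjusted result would appear by chance in about 14% of trials under the protocol's wording and almost never under a literal reading of the SAP's. The two wordings conflict. Adjustment should not depend on the test under either one.

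**What to change.** Before unblinding, amend the SAP as follows:

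1. Add baseline WOMAC A1 and baseline-by-visit to the primary longitudinal model and to the secondary contrasts drawn from it.
2. Name baseline WOMAC A1 as a predictor in the week-26 imputation model, so that the imputation and analysis models agree.
3. Delete the p<0.05 trigger from SAP 13.4.1 and Protocol 11.10. This also removes the conflict between "and" and "or".
4. Keep two fixed sensitivity analyses that are always reported: the unadjusted change-score model, and the adjusted model with age and gender added.

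The cost is SAP wording with a matching protocol edit, two model terms (about one degree of freedom per visit) and one named imputation predictor. No new data are needed. No subject is lost, because a subject without a baseline has no change score either.
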